## METHODS

### **Preoperative evaluation of the patients:**

Evaluation of the patients will be carried out on the day before surgery through proper history taking, clinical examination, complete blood count (CBC) and needed laboratory investigations according to the patient status. Plain X ray chest and ECG will be done for patients above 40 years. All patients will be informed with the procedure of US guided deep ESPB block and they will be trained to use the visual analogue scale (VAS) which consists of 10 cm line, 0 equivalent to no pain and 10 denoting the worst imaginable pain.

### **Preanaesthetic preparation and premedication:**

On arrival to the operative theatre a peripheral venous catheter will be inserted to all patients, multichannel monitor (Vamos- Dragar-Germany) will be attached to the patient to display ECG (lead II), heart rate (beats/min), non-invasive mean arterial blood pressure (mmHg) and peripheral oxygen saturation (SpO2%). All patients will receive midazolam (0.05mg/kg) and fentanyl (0.5 $\mu$ g/kg) intravenously 3 minutes before performance of the block.

### **Technique of ultrasound guided deep ESPB block:**

Ultrasound guided deep ESPB block will be performed in the block room at Medical Research Institute hospital. Patients will be placed in the prone position and a high-frequency linear probe (L 6-12MHz) of SonoSite, S nerve, 2 D machine, USA will be sterilized. After skin sterilization, the ultrasound probe will be placed 2.5–3 cm laterally to the spinous process in a parasagittal oblique plane, at the seventh cervical vertebra and moved caudally till T4.

After anatomical scanning and identification of the transverse process of T4 and the three muscles (Trapezius, Rhomboid major and Erector spinae), 2 ml of lidocaine 2% will be used to numb the skin then 18-gauge Tuohy needle will be advanced cranio-caudally towards the lateral border of transverse process of T4 using the in-plane technique.

The needle tip will be located in the fascial plane between the transverse process and erector spinae muscle. The correct needle position will be tested by injecting 2 ml of saline resulting in hydrodissection of the plane followed by the injection of:

- 20 ml bupivacaine 0.25% and 5 ml of radiocontrast dye (Omnipaque) in group 1.
- 40 ml bupivacaine 0.125% and 5 ml of radiocontrast dye (Omnipaque) in group 2.

Then, insertion of epidural catheter 2 to 3 cm over the tip of the Tuohy needle under real-time US guidance will be done.

#### **Assessment of deep ESP sensory block:**

Field of sensory block from T1 to T6 will be assessed bilaterally every 3 minutes for 15 minutes after deep ESPB using a piece of cotton soaked in iced water. The adequacy of sensory block T1-T6 will be determined before induction of general anaesthesia.

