## INTRODUCTION

Breast cancer is the commonest cancer among Egyptian females (38.8%) and modified radical mastectomy (MRM) is the most common surgical intervention.

Breast cancer surgery induces marked acute nociceptive and neuropathic pain in the chest wall, axilla and ipsilateral arm. Effective postoperative balanced analgesia including regional anaesthesia suppresses the surgical stress response and diminishes opioids needs.

The commonest reasons for overnight stay after breast cancer surgeries are postoperative pain, nausea and vomiting and anxiety. Postoperative hospital stay for breast cancer patients has shortened owing to not only the less invasive surgical technique, but also the efficient pain relief protocols including regional anaesthesia.

Ultrasound-guided fascial plane blocks are novel techniques which showed effectiveness in managing post-mastectomy pain.

Erector spinae plane (ESP) block is one of the fascial plane blocks; its efficacy depends on the compartmental spread and the local anaesthetic (LA) distribution to nearby target nerves. The absorption and diffusion of the LA has a role in determining the quality of ESP block. LA may diffuse anteriorly to the ventral and dorsal rami of the spinal nerves and through the intertransverse connective tissue to enter the thoracic paravertebral space.

Local anaesthetic volume and concentration are important factors for unilateral ESPB with volumes ranging from 10 to 40 mL have been used. However, the optimum volume and concentration, distribution and dermatomal coverage is still undetermined.

As the erector spinae fascia extends from the nuchal fascia cranially to the sacrum caudally, local anaesthetic agents extend through several levels, and the block can be effective over a large area.

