## **AIM OF THE WORK**

The aim of the present study is to evaluate the effect of US guided unilateral ESPB using different volumes of local anaesthetic on analgesic efficacy, dermatomal spread and immunomodulation in breast cancer surgery.

The primary outcome is the analgesic efficacy of the different local anaesthetic volumes of ESPB.

The secondary outcomes are the dermatomal dye spread and sensory coverage, immunomodulation and complications in breast cancer surgery.

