#### **Assessment of ES dye spread:**

After deep ESPB, patients will be transferred to the radiology suite where a CT scan of the thoracic region will be performed. The spread of the injected solution in the deep ESP will be evaluated using DICOM image processing for Mac (OsirixX, PixmeoSARL; Bern, Switzerland) and a three-dimensional digital reconstruction of the distribution of the injected contrast will be obtained.

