## Measurements

The following measurements will be carried out:

**1. Patient demographics** including age, sex and weight.

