## 6. CT scan for the spread:

Patients will be imaged 15 minutes after the block and before induction of general anaesthesia and surgery. 3 D reconstruction of the image will be done then Craniocaudal spread of the contrast and spread to Paravertebral space, epidural space or rami of the spinal nerves will be assessed and recorded.

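### Sensory block is tested only from T1 to T6, so the secondary outcome of sensory coverage cannot record spread, or a 20 ml versus 40 ml difference, outside those six segments

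*Protocol*

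**What the plan says.** Aim of the Work sets out to study the block "using different volumes of local anaesthetic on analgesic efficacy, dermatomal spread and immunomodulation in breast cancer surgery". It then lists the secondary outcomes: "The secondary outcomes are the dermatomal dye spread and sensory coverage, immunomodulation and complications in breast cancer surgery". Neither sentence restricts the levels of interest. The Introduction gives the reason for asking, namely that "the optimum volume and concentration, distribution and dermatomal coverage is still undetermined".

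Under Assessment of deep ESP sensory block, the Methods describe how sensation is tested: "Field of sensory block from T1 to T6 will be assessed bilaterally every 3 minutes for 15 minutes after deep ESPB". The test is cotton soaked in iced water. The following sentence repeats the range for a different purpose: "The adequacy of sensory block T1-T6 will be determined before induction of general anaesthesia".

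Dye is handled separately. Under Assessment of ES dye spread, patients go to radiology, "where a CT scan of the thoracic region will be performed". Measurements item 6 records craniocaudal contrast spread without a T1-T6 limit and fixes the time: "Patients will be imaged 15 minutes after the block and before induction of general anaesthesia and surgery".

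**The concern.** The test window suits a check that the block covers the operative field. It does not suit a comparison of how far two volumes extend, because it stops at fixed levels whether or not the block does. The injection is at T4, so only two segments below it are examined. Any effect of volume below T6, or above T1, goes unrecorded.

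This is a limit on data collection. Once the patient is anaesthetised the untested dermatomes cannot be recovered, so a statistical analysis plan cannot repair it.

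The main risk is a misleading contrast between the two spread measures. Contrast is followed over the thoracic region, while sensation is followed over 6 of the 12 thoracic levels. If 20 ml already reaches T6 in many patients, the trial could report that volume changes dye spread but not sensory coverage, when the second half of that statement comes from where testing stopped.

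**Working it through.** **Is there any other sensory test?** The Measurements section opens with "The following measurements will be carried out" and has eight items: demographics, vital signs, sedation, pain, post-block complications, CT, immunology and satisfaction. None maps the block. The DN4 examination questions under pain concern the painful area 10 days after surgery, so they do not map it either. The T1-T6 test is therefore the only source for sensory coverage.

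**What the window can record.** Let u be the number of blocked segments above T4 and d the number below.

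- True extent = u + d + 1
- Recorded extent = min(u, 3) + min(d, 2) + 1, so the maximum is 3 + 2 + 1 = 6

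| True block | u, d | True segments | Recorded |
|---|---|---|---|
| T2-T6 | 2, 2 | 5 | 2 + 2 + 1 = 5 |
| T2-T10 | 2, 6 | 9 | 2 + 2 + 1 = 5 |
| T3-T8 | 1, 4 | 6 | 1 + 2 + 1 = 4 |

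The first two patients differ by four segments and are recorded identically.

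**How much could be lost?** The protocol gives no expected extent, standard deviation or power for this outcome, so there is no figure to reproduce. The following is an illustration on assumed inputs. The number per group (20) and the injection level (T4) come from the protocol. The means, and a standard deviation of 1.5 segments in each direction, are assumptions. u and d are drawn as normal values, rounded and floored at 0. Groups are compared by a Welch t-test at two-sided 0.05. Power figures are good to about one percentage point.

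| Average block, 20 ml vs 40 ml | True difference | Recorded difference | Power, full extent | Power, recorded |
|---|---|---|---|---|
| T3-T5 vs T2-T6 | 1.7 | 1.2 | 79% | 73% |
| T2-T6 vs T1-T7 | 1.9 | 0.9 | 80% | 65% |
| T2-T6 vs T2-T8 (caudal only) | 1.9 | 0.5 | 84% | 21% |
| T2-T8 vs T2-T10 (caudal only) | 2.0 | 0.1 | 85% | 5% |
| T3-T5 vs T1-T5 (cranial only) | 1.8 | 1.3 | 85% | 83% |
| T3-T6 vs T1-T6 (cranial only) | 1.8 | 1.3 | 81% | 87% |

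The last row shows that recorded power can even rise slightly, because truncation also reduces the spread of the data. The recorded difference still shrinks in every row.

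With a standard deviation of 1.0 per direction, the first four rows give power of 99% to 98%, 99% to 92%, 99% to 19% and 99% to 5%.

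A simpler model gives the same picture. It takes the total count with standard deviation 2, a true difference of 2 and a cap at 6. Power of about 86% falls to 73%, 58%, 36% and 9% as the 20 ml mean rises through 5, 6, 7 and 8 segments.

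**The case against.** The best counter-argument is that the protocol leaves extent to the CT. In the secondary outcome the word dermatomal is attached to the dye, and the CT measures craniocaudal spread without the T1-T6 limit. Sensory coverage could then mean coverage of the surgical field, with T1-T6 chosen deliberately. On that reading the outcome is loosely worded but correctly measured.

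The reading is possible, but the text does not say it. Aim of the Work sets no T1-T6 limit, and the Introduction treats the extent of sensory coverage as an open question. The CT shows where contrast goes, not where sensation is lost, and the protocol names both.

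A second objection is that the power figures rest entirely on assumed extents and that the two worst cases put all the added spread below T4. This stands. If the added spread is cranial, the window may cost no power. Concentration also halves as volume doubles, so wider dye need not mean wider sensory loss. The figures show what the window can do, not what it will do.

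Third, the false conclusion needs several conditions: 20 ml must often reach T6, 40 ml must extend sensory loss further, and the authors must read a T1-T6 result as total extent. This also stands, and it limits the weight of the point.

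**Conclusion.** The concern holds. As written, the plan records sensory coverage only within T1-T6, while the stated outcome has no such limit. Differences inside the window can still be seen; those outside it are lost. Neither the direction nor the size of the loss can be predicted from the protocol. In the illustration it ranges from no loss of power to near-total loss, with the recorded difference smaller than the true one in every case. The finding that blocks of different extent get the same record needs no assumption; the power figures depend on the assumed extents and standard deviations. One secondary outcome is affected; the primary outcome and the CT outcome are not. The change should be made, but the trial does not depend on it.

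**What to change.** Keep T1-T6 as the adequacy check before induction. At the last sensory assessment before the CT, continue the same iced-cotton test cranially and caudally on both sides until normal sensation is found. Record the upper limit, the lower limit and the number of blocked segments, and compare these between Groups I and II.

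The cost is one short additional test in each of the 40 block patients, with the same material, and a sentence in the protocol. The practical difficulty is timing: the final sensory test and the CT both fall 15 minutes after the block, with a transfer to radiology between them. The mapping must be fitted around the CT, at the same time after the block in both groups.

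If this is not feasible, rename the outcome as coverage of T1-T6 and state that no conclusion will be drawn about total sensory extent. That costs only a change of wording.

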#### **Assessment of ES dye spread:**

After deep ESPB, patients will be transferred to the radiology suite where a CT scan of the thoracic region will be performed. The spread of the injected solution in the deep ESP will be evaluated using DICOM image processing for Mac (OsirixX, PixmeoSARL; Bern, Switzerland) and a three-dimensional digital reconstruction of the distribution of the injected contrast will be obtained.

#### **Anaesthesia**

All patients will receive standardized anaesthetic technique. General anaesthesia will be induced in each group by intravenous fentanyl 1 $\mu$ g/kg, propofol (2.5 mg/kg) and cisatracurium (0.15 mg/kg) to facilitate endotracheal intubation. Anaesthesia will be maintained with isoflurane (1.2 – 1.5%) and

oxygen/air mixture (50 %, 50 %). Incremental doses of cisatracurium 0.03 mg/kg will be given to maintain anaesthesia guided by train of four (TOF) count using the nerve stimulator module of (TOF watch –Organon-Ireland). Ventilation will be maintained at a tidal volume of 6 ml/kg and a rate to adjust the end-tidal carbon dioxide at (35-40 mmHg) using the ventilator (Fabius GS-Dräger-Germany).

At the end of surgery, anaesthesia will be discontinued, residual neuromuscular block will be antagonised by atropine 0.01 mg/kg and neostigmine 0.04 mg/kg, the trachea will be extubated and patients will be transferred to the postoperative anaesthesia care unit (PACU) for the next 24 hours.

### **Postoperative analgesia:**

Bolus of bupivacaine, with the same volume and concentration assigned to each group, will be given in the epidural catheter at the end of surgery in groups I & II.

In the PACU, pain score (as with other measurements) will be assessed by a physician not involved in the study design.

Intravenous morphine patient controlled analgesia (PCA) will be prepared by 50 mg morphine +45 ml normal saline with a concentration of 1 mg morphine /1 ml.

1. Bolus dose of 0.05 mg/kg.
2. Lockout Interval: 10 minutes.
3. Four hourly limiting doses will be 10 mg.

If VAS still  $\geq 4$ , patients will be administered Ketorolac 30 mg IV as rescue analgesia.

### **Natural killer cells isolation and cytotoxicity assay:**

Samples of 1 ml of patients' peripheral blood will be collected on EDTA for flow cytometry to enumerate for both cytotoxic lymphocyte populations (NK cells

12.  
and cytotoxic t lymphocytes (Ctls)). CD 56 will be used as a marker for NK cells, while CD 8 will be used as a marker for Ctls.

Cytotoxicity assay will be done by measuring the release of lactate dehydrogenase (LDH) from non-viable cells (Cytotoxicity Detection Kit, 630117; Clontech Laboratories, Mountain View, California) according to the manufacturer's instructions. Then ratio of LDH released specifically from NK cells will be correlated according to the results of flow cytometry.

## Measurements

The following measurements will be carried out:

**1. Patient demographics** including age, sex and weight.

**2. Vital signs:**

1. Heart rate (beats/min) and ECG will be continuously monitored and will be recorded before induction of anaesthesia, every 15 minutes intraoperatively and at arrival to the PACU, then every 4 hours for the first 24 postoperative hours with recording of any abnormalities.
2. Peripheral oxygen saturation ( $\text{SpO}_2\%$ ) will be continuously monitored and will be recorded before induction of anaesthesia, every 15 minutes intraoperatively and at arrival to the PACU, then every 4 hours for the first 24 postoperative hours.
3. Mean arterial blood pressure (MABP) in mmHg will be monitored and recorded before induction of general anaesthesia, every 15 minutes intraoperatively and at arrival to the PACU, then every 4 hours for the first 24 postoperative hours.
4. Postoperative respiratory rate will be recorded every hour for the first 4 hours and then every 4 hours for the rest of the 24 hours.

**3. Patient sedation scale:**

Patient sedation will be assessed by Richmond Agitation-Sedation scale in PACU every 4 hours for 24 hours.

Table (1): Richmond agitation sedation scale

Score	Term	Description
+4	Combative	Overtly combative or violent; immediate danger to staff
+3	Very agitated	Pulls on or removes tube(s) or catheter(s) or has aggressive behaviour toward staff
+2	Agitated	Frequent nonpurposeful movement or patient–ventilator dyssynchrony
+1	Restless	Anxious or apprehensive but movements not aggressive or vigorous
0	Alert and calm	Spontaneously pays attention to caregiver
-1	Drowsy	Not fully alert, but has sustained (more than 10 seconds) awakening, with eye contact, to voice
-2	Light sedation	Briefly (less than 10 seconds) awakens with eye contact to voice
-3	Moderate sedation	Any movement (but no eye contact) to voice
-4	Deep sedation	No response to voice, but any movement to physical stimulation
-5	Unarousable	No response to voice or physical stimulation

#### 4. Pain assessment:

1. Acute postoperative nociceptive pain will be measured by:
  - a. Visual analogue scale (0-10) where 0=no pain, 10=worst imagineable pain every hour for the first 4 hours and then every 4 hours for the rest of the 24 postoperative hours. This will be done during rest and movement.
  - b. Total amount of IV morphine will be calculated at the end of the 24 postoperative hours.
  - c. Total amount of rescue analgesia will be calculated and first time of its need will be recorded.
2. Acute postoperative neuropathic pain will be detected 10 days after surgery by DN4 (Douleur Neuropathique 4) questionnaire (10 Questions with cut-off value 4/10).

## DN4 - QUESTIONNAIRE

To estimate the probability of neuropathic pain, please answer yes or no for each item of the following four questions.

### INTERVIEW OF THE PATIENT

#### QUESTION 1:

Does the pain have one or more of the following characteristics?	YES	NO
Burning .....		
Painful cold .....		
Electric shocks .....		

#### QUESTION 2:

Is the pain associated with one or more of the following symptoms in the same area?	YES	NO
Tingling .....		
Pins and needles .....		
Numbness .....		
Itching .....		

### EXAMINATION OF THE PATIENT

#### QUESTION 3:

Is the pain located in an area where the physical examination may reveal one or more of the following characteristics?	YES	NO
Hypoesthesia to touch .....		
Hypoesthesia to pinprick .....		

#### QUESTION 4:

In the painful area, can the pain be caused or increased by:	YES	NO
Brushing? .....		

YES = 1 point

NO = 0 points

Patient's Score: /10

Before patients would be discharged home, DN4 questionnaire will be explained to every patient. Postmastectomy neuropathic pain will be detected in breast, axilla or arm. Its onset (days) and interference with work, sleep or mood will be recorded.

## 5. Post-block complications:

Any complications after the block will be spotted and recorded:

1. Symptoms or signs of local anaesthetic toxicity (tinnitus, perioral numbness, seizure).
2. Postoperative nausea and or vomiting (PONV) score:
  1. None.
  2. Yes, and relieved by treatment.
  3. Yes, but not relieved by treatment.

Intravenous metoclopramide (10 mg) and ondansetron (4 mg) will be given as the first and second line of treatment of vomiting, respectively.

3. Arrhythmias.
4. Haematoma at the site of injection.
5. Respiratory depression (when respiratory rate < 8 breath / min).

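### The three PONV codes are not exhaustive: nausea or vomiting that goes untreated has no true code

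*Protocol*

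**What the plan says.** The item is in the Protocol under Measurements, section 5 (Post-block complications), as the second entry in the list. It is titled "Postoperative nausea and or vomiting (PONV) score", so nausea without vomiting counts as an event.

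The score has three codes. Code 1 is the absence of an event. Code 2 reads "Yes, and relieved by treatment" and code 3 reads "Yes, but not relieved by treatment".

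One sentence on antiemetics follows. It names two drugs, which "will be given as the first and second line of treatment of vomiting, respectively". Nausea does not appear in that sentence. Nowhere else does the Protocol give an antiemetic instruction or a rule for coding PONV; the only other mention of nausea is background in the Introduction.

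Complications are one of the secondary outcomes listed under Aim of the Work: "The secondary outcomes are the dermatomal dye spread and sensory coverage, immunomodulation and complications in breast cancer surgery".

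**The concern.** A categorical outcome should give every patient exactly one true category. Here the two positive codes combine two facts: whether an event occurred, and how it responded to treatment. A patient who had an event and was not treated satisfies the first fact, but the second does not apply to her. The scale has no place for her.

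The treatment sentence makes this more than a remote possibility. The score covers nausea and/or vomiting, while the sentence covers vomiting, so the two scopes differ within one list item.

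What is at stake is the PONV comparison across three groups. If an untreated event is entered as code 1, it disappears from the count. If it is entered as code 3, it joins the worst category. These errors run in opposite directions, and different assessors may settle the matter differently. The loss happens when the form is filled in: a later analysis plan cannot tell a true absence from an untreated event, or a true treatment failure from an untreated one.

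**Working it through.** The Protocol states no figure to reproduce here. The check compares the possible patient states with the codes, followed by one line of arithmetic.

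**Inputs**
- Scope of the score: nausea and/or vomiting (Measurements, section 5).
- Codes: 1 no event; 2 event, relieved by treatment; 3 event, not relieved by treatment (same section).
- Scope of the antiemetic sentence: vomiting (same section).
- Group size: 20 patients in each of three groups (Patients).

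**Patient states against codes**

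| State | Code 1 true? | Code 2 true? | Code 3 true? |
|---|---|---|---|
| No nausea, no vomiting | Yes | No | No |
| Event, treated, relieved | No | Yes | No |
| Event, treated, not relieved | No | No | Yes |
| Event, untreated | No | No | Only if *not relieved by treatment* is stretched to mean *not treated* |

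The first three states each have one true code. The fourth has none.

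**Who falls in the fourth row**
- If the antiemetic sentence is read literally, as applying to vomiting only: nausea without vomiting, for which the Protocol specifies no antiemetic, plus any vomiting that stops before treatment or for which the patient declines it.
- If *vomiting* is read as shorthand for nausea and/or vomiting: events that resolve before treatment, or for which treatment is declined.

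The row is smaller on the second reading, but the Protocol rules it out on neither.

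**Size per patient**
- 1 patient / 20 patients = 0.05, or 5 percentage points of a group's rate.
- Entered as code 1: the group's recorded PONV rate is 5 points too low for each such patient.
- Entered as code 3: the recorded PONV rate is right, but the rate of unrelieved PONV is 5 points too high for each such patient.

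The number of such patients would require a PONV rate and the share of events left untreated. The Protocol gives neither, so the total effect cannot be computed.

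**The case against.** The strongest reply is that the antiemetic sentence sets the order of two drugs and does not say that nausea is left untreated. It sits directly beneath a score that covers both symptoms, and since both positive codes assume treatment, the authors may well have meant any PONV to be treated. This stands as far as it goes. A reader might infer that every patient with nausea alone receives no antiemetic, but the text is silent on that and does not support the inference. The reply still does not make the scale exhaustive, because an event that resolves untreated or for which treatment is declined has no code under the generous reading either.

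A second reply is that the assessor is not forced to choose between codes 1 and 3. The item could be left blank, code 2 might be used if the nausea settles, and the section also states "Any complications after the block will be spotted and recorded", so the event could be noted outside the score. This also stands: miscoding is a risk, not a certainty. But none of these routes gives a true value of the score, and the Protocol gives no rule for choosing among them.

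A third reply is that the point is small: one item among several complications, within one of several secondary outcomes. That is right, and it limits the weight of the point. The primary analgesic outcome and the sample size are unaffected.

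A reader might also infer from the section's heading that Group III, which has no block, is left out of PONV recording. The documents do not support this. The item itself is labelled postoperative, the Measurements section is introduced without any restriction by group, and Aim of the Work speaks of complications in breast cancer surgery generally.

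**Conclusion.** The point holds in a limited form. The three codes do not cover an untreated event, and the scope of the score does not match the scope of the only treatment sentence. This follows from the text alone and needs no assumed rate.

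The consequence, entry as no event or as treatment failure, is possible rather than established. Its size is 5 percentage points of a group's rate per affected patient, on the planned 20 per group. A reader might go further and put a total bias on the PONV comparison by assuming an incidence and a share left untreated. Neither figure is in the Protocol, and the share depends on how the treatment sentence is read, so no total is given here.

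The matter is worth correcting before data collection because the rule is fixed in the Protocol, the lost information cannot be recovered later, and the correction is cheap.

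**What to change.** Record four items separately for every patient: nausea (yes/no), vomiting (yes/no), antiemetic given (yes/no) and, where one was given, response (relieved/not relieved). This keeps occurrence apart from treatment and lets any summary score be derived afterwards. The minimum alternative is to add one code to the present score for an event that was not treated.

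The sponsor should also reconcile the score, which covers nausea and/or vomiting, with the treatment sentence, which covers vomiting. Which clinical rule should apply is for the sponsor to decide and is not proposed here.

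The cost is a few tick-boxes on the form, or one extra code, and a sentence or two in the Protocol. The downside is that the score would no longer match the three-level version now in the Protocol, although those levels remain derivable for treated patients.
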